14.6 Exclusions- Bipolar and Psychosis

If a potential recruit is excluded on the basis of a self-reporting at the screening questionnaire a previous diagnosis of Bipolar disorder or psychosis then would be automatically provided with the following information:

Screening website automated message for bi-polar disorder:

"You have reported that you have previously received a diagnosis of either bipolar disorder or psychosis.

Because this study is focused on enhancing resiliency and preventing poor mental health in the future, rather than treating current difficulties, the current study is not suitable for you at this time. The resiliency treatment has not been designed to help with these difficulties so we are sorry to say that taking part in the study would not be in your best interests at this time. Thank you for your interest.

Your GP or relevant medical professional is the best person to decide what help you need.

You can contact your GP using the normal telephone number for your GP practice. If the surgery is not open, you will either be re-directed automatically to the out-of-hours GP service or you will be given another number to call. You can also **phone 111 to access the NHS 111 service**, which provides access to local NHS healthcare services in England, and is available 24 hours a day, 365 days a year.

Alongside your GP, there are other services available to you to provide information and support:

Useful **WEBSITES** that you can access directly below include:

- YoungMinds are there to make sure all young people get the best possible mental health support and have the resilience to overcome life's difficulties. They provide lots of resources to help with young person's mental health: https://youngminds.org.uk/find-help/
- Mind The Mental Health Charity provide information, advice, and support to empower anyone
 experiencing a mental health problem. They provide information about mental health problems
 and potential treatments as well as tips for everyday living. https://www.mind.org.uk/
 - o **For bipolar disorder:** https://www.mind.org.uk/information-support/types-of-mental-health-problems/bipolar-disorder/about-bipolar-disorder/?o=1142#.XGQJJVX7SUk
 - For psychosis: https://www.mind.org.uk/information-support/types-of-mental-health-problems/psychosis/#.XGQI_IX7SUk
 - o **For schizophrenia**: https://www.mind.org.uk/information-support/types-of-mental-health-problems/schizophrenia/about-schizophrenia/?o=6266#.XGQJQIX7SUk
 - For apps to help with your wellbeing and mental health:
 https://www.mindcharity.co.uk/advice-information/how-to-look-after-your-mental-health/apps-for-wellbeing-and-mental-health/
- BipolarUK National charity dedicated to supporting individuals with bipolar, their families and carers. Their websites has information leaflets and links to support, including a peer support line https://www.bipolaruk.org/
- Rethink Mental Illness. Provide expert advice and information to everyone affected by mental
 health problems, and provide services and groups; including resources specific to young people
 https://www.rethink.org/living-with-mental-illness/young-people
 - Toolkit for young people with questions or worries about their mental health: https://www.rethink.org/media/1020652/ResourceFinal.pdf
- There are a series of NHS self-help guides which can be found here https://web.ntw.nhs.uk/selfhelp/

There are more guides and online courses here:
 https://www.cci.health.wa.gov.au/Resources/Looking-After-Yourself

Alternatively, here are **HELPLINES** you can ring to talk to someone about what how you are feeling

- Papyrus [name] or text: [name] offers National support to young people up to age 35 who are feeling suicidal. (Monday-Friday 10:00am-5:00pm and 7:00pm-10:00pm; 2:00pm-5:00pm on weekends, [contact]
- The **Samaritans [name]** Freephone (UK and Republic of Ireland): [name] (24 hours), offer a confidential service so you can talk about your feelings, you can contact them at www.samaritans.org, Email: [contact]
- **SANE** offers support to anyone coping with mental illness, including concerned relatives or friends. The SANE helpline **[name]** is available 7 days a week from 6.pm-11 pm
- Maytree is a registered charity supporting people in suicidal crisis and is open for calls and emails 24 hours a day. [name], [contact]
- Young Minds Crisis Messenger provides free, 24/7 crisis support across the UK if you are experiencing a mental health crisis. If you need urgent help text YM to [name]. Texts are free from EE, O2, Vodafone, 3, Virgin Mobile, BT Mobile, GiffGaff, Tesco Mobile and Telecom Plus.
- **CALM [name]** (Daily 17:00-midnight) Offers support to young men in the UK who are down or in a crisis, www.thecalmzone.net
- The Mix, Freephone: [name] (13:00-23:00 daily), If you're under 25 you can talk to The Mix for free on the phone, by email or on their webchat. You can also use their phone counselling service, or get more information on support services you might need. www.themix.org.uk

If you find your symptoms particularly distressing or have thoughts about ending your life then please go to the nearest emergency room, or immediately contact your GP.

Talking to people who understand can make it much easier to manage your symptoms so **please do call your GP or one of the specialist helplines above**.

14.7 Risk Assessment and Reporting SOP

All researchers and clinicians that have direct contact (by telephone or email) with recruits or participants will be familiar and trained how to use this SOP and will sign the delegation log to say that this has been done. The purpose of the SOP is to script the contact between researcher and participant so that the risk is assessed.

Pls/supervisors/clinicians (e.g., local psychiatrists or clinical psychologists) will also familiarise themselves with this SOP and provide researchers with their contact details in case the researcher needs advice. When clinical academic staff are away on leave they should ensure appropriate cover is arranged to support researcher with advice on for any risk issues that might arise in their absence. The clinician is available to support and guide the researcher in responding to risk and where requested in communicating and providing guidance to the participant.

14.8 Telephone contact

When conducting telephone interviews or providing on-demand telephone support in which risk may be disclosed, the interviewer should establish the telephone number and location of the participant at the start of the call, and clarify the boundaries of confidentiality:

'Hi, is that (name) this is X from the Nurture-U Bounce-Back trial, is now a convenient time to talk?' [or in response to answering a call direct from a participant – at which point we would ask for name and email, so we can identify them]

If yes 'This call is confidential and the only reason I would break that is if I thought you were at risk to yourself or others and it was in your best interests.

We just wanted to give you a call after your message to us in the email you sent / I would like to clarify what you are telling me now on the phone.

Can I just check where you are at the moment? [obtain details of location/address]

"I see that you've said / you mentioned that....... (examples: if thoughts of death /"what is the point?" / "it might be better if I did not wake up",

"Has this gone as far as thinking about harming yourself or killing yourself?" If yes, or if already stated:

'These are common thoughts and can vary a lot in their severity and it's important to make sure you are receiving the right kind of support. So I would now like to ask you some more questions that will explore these feelings in a little more depth."

INTENTION

Have you had any intention to hurt or kill yourself? YES OR NO

PLANS

1 Do you know how you would kill yourself?

Yes / No

If yes – ask for and record details

2 Have you made any actual plans to end your life?

Yes / No

If yes – ask for and record details

ACTIONS

3. Have you made any actual preparations to kill yourself? Yes / No

If yes - ask for and record details

4. Have you ever attempted suicide in the past?

Yes / No

If yes - ask for and record details

6. **PREVENTION** Is there anything stopping you killing or harming yourself at the moment? Yes / No

If ves – ask for and record details

7. Do you feel that there is any immediate danger that you will harm or kill yourself?

Yes / No

Ask for and record Details:

If yes to any of questions 1-4

- [if yes to 4 only, or yes to 1 only] I can see that things have been very difficult for you, but it seems to me these thoughts about death are not ones you would act on would this be how you see things? (if they say yes) I would advise you to make an appointment to see your GP to talk about these feelings.
- [if any of 1-3] Would you like us to write a letter to your GP letting them know how you are feeling? If yes, please can you give us your permission to do so (and provide their contact details)
- [all] I can also email you a list of website and helplines for people that have expertise at helping in just this kind of situation, would that be helpful?

If yes to 2 and 3 or to 6, request clinical input if not a clinician and say the following

- I am very concerned about your safety at this moment....
- I am not a clinician, but I would like you to talk to one right now. With your permission I am going to call the site clinician/your GP to let them know how you are feeling and to arrange for you to receive immediate help/a call back. Can you provide their contact details?

In addition, If yes to question 6 [immediate risk]

• I think its best that you get emergency support at this time. I am going to call your GP/the emergency services and send them to your location.

Keep the participant on the phone while you call the clinician from another number or email.

If immediate risk is disclosed the interviewer should not hang up if at all possible.

In case contact is lost, the participant should be informed that the interviewer / supervisor will call them back straight away but that if they are unable to make contact the participant's G.P. or the emergency services will be informed. Good practice is to call /use a phone line for participants that (a) is mobile so that researcher can contact clinical supervisor if physically proximal (b) have a second line to contact clinical supervisor (e.g., by text) whilst maintaining conversation with participant.

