standardized measures or contacts initiated by the participant. If the researcher has serious concerns about a participant, where appropriate, after discussion with the clinician, the clinician will contact the participants (by email, telephone) to review the situation, provide guidance and offer to write a referral letter, subject to participant consent. These procedures will be made explicit in all information sheets. Any concerns detected this way will be recorded on a standardised pro forma, a copy which will be sent to the sponsor for the trial. The same process will be activated in response to any concerns raised by participants at other times, either spontaneously or in responses during the assessments. We will record both serious and non-serious adverse events as defined by the National Research Ethics Service (e.g. deaths; self-harm; serious violent incidents, referral to crisis care or admission to psychiatric hospital) within both groups and report them to the Research Ethics Committee to determine whether events are related to the treatments and to take appropriate action.

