14.10 Risk register

All risk alerts whether via email or telephone contact will be logged on a risk register with any action taken, by whom and when (see below). Site researchers will follow up on risk alerts within 1 working day using the risk assessment and reporting SOP including responding to participant and registering the action taken. This will need to be logged at each local site and shared centrally with the lead site (Exeter) in an anonymised format.

14.11 Action to take after responding to immediate risk:

- 1. Document action taken on the risk log and a risk report form (see below).
- 2. Send letter electronically or by post to GP documenting information gathered and action taken.
- 3. Seek / offer supervision around support and debriefing as appropriate.

Figure 3

Risk Report Form

Participant Trial Number

Supervisor:	Signed:	Date://_	
Researcher / assessor / supporting PWP: _	Signo	ed: Date:	//
Date action taken://			
Additional notes / actions taken:			
Date reported://			
Immediate risk:			
Prior attempts:			
Prevention:			
Actions:			
Plans:			
Suicide risk information: [note answers to Intention:	all questions above re	e yes/no answers and (details]

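### In the 14.8 telephone risk script both escalation rules cite question 6, the protective question; immediate danger is question 7 and no numbered rule cites it

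*Protocol*

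**What the plan says.** Section 14.8 of the Protocol gives a scripted telephone risk assessment. After an unnumbered question on intention, it prints questions numbered 1, 2, 3, 4, 6 and 7; there is no 5. Questions 1 and 2 concern plans, 3 preparations and 4 past attempts. Question 6, headed PREVENTION, reads "Is there anything stopping you killing or harming yourself at the moment? Yes / No". The next reads "7. Do you feel that there is any immediate danger that you will harm or kill yourself".

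The actions then follow by number:

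- The lower tier (advice to see the GP, the offer of a letter to the GP, a list of helplines) is headed "If yes to any of questions 1-4".
- The clinical-input rule reads "If yes to 2 and 3 or to 6, request clinical input if not a clinician and say the following".
- The emergency rule opens "In addition, If yes to question 6 [immediate risk", with the bracket closing after that label. Its action is to send help to the participant's location.

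Section 14.7 says the purpose of the SOP is to script the contact so that risk is assessed. Section 14.10 makes it the working tool: "Site researchers will follow up on risk alerts within 1 working day using the risk assessment and reporting SOP". Section 14.9 applies similar actions to risk disclosed by email.

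**The concern.** A yes to question 6 means that something is holding the participant back. That is reassuring, yet it is the answer to which both escalation rules are tied. A yes to question 7 is the most serious answer in the list, and no numbered rule refers to it. A caller who applies the script by number would escalate for the wrong answer and could fail to escalate for the right one.

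What is at stake is participant safety, not inference. The caller need not be a clinician: the script includes a line in which the caller says so. It would be used live with someone disclosing suicidal thoughts, when there is little time to work out what a digit was meant to be.

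**Working it through.** There is no planned figure to reproduce. The check sets each numbered rule in 14.8 against the printed questions.

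**Rules against questions**

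| Rule in 14.8 | Questions cited | Names 6 (PREVENTION)? | Names 7 (immediate danger)? |
|---|---|---|---|
| Heading of the lower-tier advice | any of 1 to 4 | no | no |
| Advice to see the GP | 4 alone or 1 alone | no | no |
| Offer of a letter to the GP | any of 1 to 3 | no | no |
| Clinical input | (2 and 3) or 6 | yes | no |
| Emergency support | 6 | yes | no |

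Question 6 is named in 2 of 5 conditions, both of them escalations. Question 7 is named in 0 of 5.

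**Two single-answer cases, followed by number**

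- Yes to 7 only: no rule fires, not even the lower tier, which needs a yes among 1 to 4.
- Yes to 6 only: clinical input and emergency support both fire.

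**All answer patterns.** Six yes/no questions give 2^6 = 64 patterns. These are logical counts, not probabilities.

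- Yes to 7: 2^5 = 32 patterns. Emergency support needs a yes to 6, so the 2^4 = 16 patterns with no to 6 miss it. These are the patterns in which the person is in danger and names nothing that stops them.
- Within those 16, clinical input is still reached where 2 and 3 are both yes: 2^2 = 4 patterns. The other 16 − 4 = 12 reach neither escalation.
- No to 7: 32 patterns. The 16 with yes to 6 trigger emergency support on the protective answer.

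**Which list do the rules fit?** Renumber the last two questions so that PREVENTION is 5 and immediate danger is 6. All five rules then make sense as printed: 1 to 4 drive the lower tier, 2 with 3 or immediate danger drives clinical input, immediate danger drives emergency support, and the protective question drives nothing. That points to a one-place numbering slip.

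**After correction.** All 32 patterns with yes to immediate danger reach both escalations. Among the 32 with no, emergency support fires in 0, and clinical input fires only through 2 and 3 together.

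**The case against.** The strongest reply is that the slip corrects itself. The emergency rule carries an immediate-risk label, only one question asks about immediate danger, and sending help would be an odd response to someone describing what keeps them safe. The clinical-input rule has no label, but the emergency rule is worded as an addition to it. The Risk Report Form in 14.11 has separate fields for prevention and immediate risk. A worded instruction in 14.8, with no number in it, tells the caller to keep the line open if immediate risk is disclosed.

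Staff are to be trained, and help does not depend on the digit. Section 14.7 says "The clinician is available to support and guide the researcher in responding to risk", and section 13.1 says "If the researcher has serious concerns about a participant, where appropriate, after discussion with the clinician, the clinician will contact the participants". Screening also excludes people who report suicide risk, so such calls should be few.

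Most of this stands, and it lowers the likelihood of harm. It does not make the rule right. In the emergency rule the number and the label contradict each other, and in the clinical-input rule there is only the number. Keeping the line open does not settle which answer calls for emergency help. One might also suspect a digit garbled in converting the PDF, but two adjacent numbers would each have to be misread by one.

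**Conclusion.** The point holds. Both escalation rules in 14.8 cite the protective question, and none of the five numbered conditions cites immediate danger. Followed by number, 16 of the 32 answer patterns with a yes to immediate danger miss emergency support, and 12 of those miss clinical input too. Those counts read the clinical-input rule as 2 and 3 together, or else 6, and give every pattern equal standing. They say nothing about how often an escalation would be missed in practice.

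The intended meaning can be recovered, and other safeguards exist, so this should be corrected but does not threaten the trial. No endpoint, sample size or analysis is affected.

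**What to change.** Either of two edits to 14.8 is enough:

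1. Change 6 to 7 in both rules, so that clinical input follows a yes to 2 and 3 or to 7, and emergency support follows a yes to 7, keeping the immediate-risk label.
2. Close the gap in the list so that PREVENTION becomes 5 and immediate danger becomes 6, and leave the rules as printed.

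Make the same change in any separate copy of the SOP, and notify anyone already trained on it. The cost is two digits and a short note, with no extra participants, data or analysis.

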14.3.2 Assessment Website at Follow-up (6 and 12 weeks)

A recruit may indicate risk on the assessment website in follow-up assessments in response to questions about suicidality. If the participant scores 1-3 on question 9 of the PHQ9, then further questions to assess risk will automatically be presented.

PHQ9; Q9

Over the last two weeks, how often have you been bothered by any of the following problems? Thoughts that you would be better off dead, or of hurting yourself in some way?

Those scores would represent the answers several days (1), more than half the days (2) and nearly every day (3)

The further risk questions which will automatically be asked:

R1 In the last 2 weeks have you been experiencing regular thoughts about suicide?

R2 In the last 2 weeks have you had any intention to hurt or kill yourself?

R3 In the last 2 weeks have you made any plans to harm yourself or end your life?

If the participant answers yes to any of those questions then they would be automatically presented with the following risk page:

Follow up Website Automated Risk Message:

"Your responses to these questions suggest you have been thinking about suicide or about hurting yourself.

These kinds of thoughts can vary a lot. This may have just been a brief passing thought or reflect a sense of feeling trapped, but without any intention to do anything. These thoughts are relatively common and not that unusual in people who feel stressed. If you would like support with these thoughts, please contact your GP or relevant medical professional;

If you feel at high risk to yourself or others, please contact your GP immediately.

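### Telephone risk script (Protocol 14.8): a caller who discloses only one of actual plans or actual preparations gets neither GP-appointment advice nor clinical input, unless 'question 6' is also answered yes

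*Protocol*

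**What the plan says.** Section 14.8 numbers its questions as follows: 1, knows how; 2, "Have you made any actual plans to end your life"; 3, actual preparations; 4, a past attempt; 6, whether anything is stopping the caller; 7, "Do you feel that there is any immediate danger that you will harm or kill yourself". There is no question 5.

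For a yes to any of 1 to 4, the scripted responses are:

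- **GP-appointment advice.** This branch opens with "if yes to 4 only, or yes to 1 only] I can see that things have been very difficult for you". The caller is then asked whether they see the thoughts as ones they would not act on, and the advice follows only on agreement: "if they say yes) I would advise you to make an appointment to see your GP to talk about these feelings".
- **Offer of a GP letter.** "if any of 1-3] Would you like us to write a letter to your GP letting them know how you are feeling".
- **Helpline and website list.** Offered to everyone in this group.
- **Clinical input.** "If yes to 2 and 3 or to 6, request clinical input if not a clinician and say the following".
- **Emergency support.** "In addition, If yes to question 6 [immediate risk", although the immediate-danger question is printed as number 7.

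On the follow-up website (section 14.3.2), three risk questions cover regular thoughts, intention and plans. The rule there is "If the participant answers yes to any of those questions then they would be automatically presented with the following risk page". That page tells people who are making plans to contact their GP urgently, and an automated record goes to the therapists and the chief investigator.

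**The concern.** A risk script should respond at least as strongly when more risk is disclosed. This one does not. The GP-advice branch is restricted to a lone yes on question 1 or question 4, and the clinical-input branch needs plans and preparations together. Callers who disclose one of those two fall between the branches.

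Section 14.7 says the SOP is there to script the contact, and the script's own lines show that non-clinicians will use it. For a participant who discloses an actual suicide plan, such a member of staff has no fixed step telling them to advise a GP visit or to bring in a clinician. The same disclosure on the follow-up website brings urgent GP advice and an alert. What is at stake is a missed or delayed escalation during a live call.

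**Working it through.** The check applies the printed rules to every combination of answers.

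**Inputs (section 14.8)**

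- GP advice = (1 only or 4 only) and the caller agrees with the check
- Letter offer = 1 or 2 or 3
- List = any of 1 to 4
- Clinical input = (2 and 3) or 'question 6'

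The unnumbered question on intention is tied to no branch. Four yes/no questions give 2^4 − 1 = 15 patterns with at least one yes.

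**No yes to 'question 6', caller agrees with the check where it is asked**

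| Pattern on questions 1–4 | Number | GP advice | Letter offer | List | Clinical input |
|---|---|---|---|---|---|
| 1 only | 1 | yes | yes | yes | no |
| 4 only | 1 | yes | no | yes | no |
| 1+4 | 1 | no | yes | yes | no |
| Exactly one of 2, 3 (2; 3; 1+2; 1+3; 2+4; 3+4; 1+2+4; 1+3+4) | 8 | no | yes | yes | no |
| Both 2 and 3 (2+3; 1+2+3; 2+3+4; 1+2+3+4) | 4 | no | yes | yes | yes |

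- Patterns that include 2 or 3: 8 + 4 = 12. Neither GP advice nor clinical input: 8 of 12.
- Adding 1+4: 8 + 1 = 9 of 15 with neither step.
- Restricted to callers who also say yes to 1: six patterns include 2 or 3, and four of them (1+2, 1+3, 1+2+4, 1+3+4) get neither.
- If '1 only' and '4 only' callers do not agree with the check, they also get neither: 9 + 2 = 11 of 15. The script has no step for a *no* to that check.

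**Effect of one added yes.** Moving from 1 only to 1+2, 1+3 or 1+4 removes the GP advice and gains nothing, because the letter offer and the list already applied. Moving from 4 only to 4+1, 4+2 or 4+3 replaces the GP advice with the letter offer.

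**Yes to 'question 6'.** Clinical input is triggered in 15 of 15 patterns, so there is no gap there.

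**Which question is 'question 6'?** The result is the same on either meaning, because it concerns only callers who do not say yes to it. On the printed numbering, a caller with a plan and nothing stopping them answers no to question 6 and does not set off the trigger.

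**Alternative reading of the trigger as 2 or 3.** Clinical input is reached in 12 of 15 patterns. Only 1+4 gets neither step, or 1 + 2 = 3 of 15 if the '1 only' and '4 only' callers do not agree with the check.

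**The case against.** The strongest objection is about reading. The trigger sentence is already misdrafted in its question number, and the tiers make more sense if either plans or preparations was meant to bring in a clinician. That may well have been the intention. But the script uses *or* and *any of* elsewhere when it means alternatives, and the sentence itself sets *and* against *or*. Staff following it would apply *and*. Even the generous reading leaves 1+4 uncovered.

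Second, these callers are not left with nothing. All nine patterns carry the offer of a GP letter and the helpline list, and a written letter is a real GP route. That stands. But the letter is optional, and a '1 only' caller is offered it too, so it does not replace the lost advice.

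Third, there is other cover:

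- Section 13.1 provides for GP guidance and clinician contact, but where judged necessary or appropriate.
- Section 14.1.2 says a clinician may make contact, and 14.7 makes one available if the researcher needs advice.
- Section 8.7 has therapists following up risk, and 13.3 treats suicidal ideation or plans as adverse events.
- Section 14.10 requires follow-up within one working day, but by this same SOP.
- The email template in 14.9 urges GP contact, which helps callers who emailed first but not those who telephone directly.
- When the person on the call is a clinician, the request for clinical input does not arise.

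These routes soften the consequence, but none fixes a step during the call. The population is also screened for depression, anxiety and suicide risk, so such calls may be few.

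Fourth, equal weighting of patterns says nothing about how often each occurs. That is correct: the counts describe the rule's coverage only.

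**Conclusion.** The point holds on the printed script and should be fixed. With no yes to 'question 6', 8 of the 12 patterns that include plans or preparations reach neither GP-appointment advice nor clinical input, and 1+4 makes 9 of 15. Greater disclosed risk can bring a weaker scripted response.

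The conclusion rests on taking *and* literally and on questions 1 to 4 as numbered. If *either* was meant, the gap shrinks to 1+4, plus the two lone-yes patterns where the caller does not agree with the check. The protocol gives no disclosure frequencies, so the number of participants affected cannot be estimated. This is a participant-safety matter in the protocol text and changes no statistical result.

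**What to change.** In section 14.8, with the clinical lead's confirmation:

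1. Change the clinical-input trigger to a yes to 2 *or* 3, or to the immediate-danger question, and correct the question 6/7 numbering there and in the emergency branch.
2. Give advice to contact the GP for any yes to questions 1 to 4.
3. Keep the check on whether the caller would act on the thoughts for '1 only' and '4 only', but do not make the GP advice depend on the answer. State what a *no* to that check triggers.

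All 15 patterns then receive GP advice or more, and no added yes removes a step.

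The cost is SOP wording, brief retraining of call staff and some additional calls to the site clinician. With no yes to 'question 6', patterns that trigger clinical input rise from 4 to 12 of 15. How many extra calls that means is unknown.

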14.9 E-mail contact

In the eventuality that participants send emails to researchers or receiving on-demand e-mail support that indicate potential elevated suicide risk (e.g. talking about death, ending it all, seeing no hope, referring to suicide or self-harm, seeing no way out), then further follow-up steps will be taken, including attempts to respond to the participant to clarify the severity of the risk. These emails will provide guidance and signposting information (replicating the information provided on the automated webpage in response to reporting suicidality on the screening/assessment website) and enquire about risk following the questions above (e.g., asking about suicidal ideation, thoughts, plans, preparation, prevention, means).

An email will be sent to participant, acknowledging their potential distress and thoughts of death and self-harm, including the following questions:

Self Risk Q1 Are you currently experiencing any thoughts about suicide?

Self Risk Q2 Do you have any intention to hurt or kill yourself?

Self Risk Q3 Have you made any current plans to end your life or harm yourself?

Self Risk Q4 Do you have the means to harm yourself or end your life?

A template email for initial response is as follows, to be adapted to directly respond to details and concerns raised in specific email from the participant:

"Dear

Thank you for contacting us.

Your email suggested that you might have been having thoughts about harming or killing yourself. These thoughts can vary a lot from person to person. These may have just been brief passing thoughts or reflect a sense of feeling trapped, but without any intention to do anything. These thoughts are relatively common and not that unusual in people who feel stressed.

On the other hand, you may have been thinking about your death a lot, or you may have thought about killing yourself. You may have even have thought about how you might kill yourself or made a plan to end your life. In any of these cases, we strongly urge you to talk to someone about these thoughts, and in particular your GP or family doctor.

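### Section 14.8 keys clinical input and the emergency step to item 6, the prevention question, although immediate danger is item 7

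*Protocol*

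**What the plan says.** Protocol section 14.7 states the role of the script: "The purpose of the SOP is to script the contact between researcher and participant so that the risk is assessed". Section 14.8 then gives the questions. An intention question without a number comes first ("Have you had any intention to hurt or kill yourself? YES OR NO"). The numbered items follow: method (1), plans (2), preparations (3), past attempt (4), prevention (6) and immediate danger (7). No item 5 is printed. Item 6 is worded "Is there anything stopping you killing or harming yourself at the moment? Yes / No", and the last item is "7. Do you feel that there is any immediate danger that you will harm or kill yourself".

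The action lines come after the questions. A first block, for a yes to any of items 1 to 4, covers advice to see the GP, an offer of a letter and a list of helplines. Two escalation lines follow. The one for clinical input is "If yes to 2 and 3 or to 6, request clinical input if not a clinician and say the following". The one for calling the GP or emergency services to the person's location is "In addition, If yes to question 6 [immediate risk", where the bracketed words are the line's own label.

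Section 14.9 covers risk raised by email. It lists four questions that the email is to contain (Self Risk Q1 to Q4) and gives a template for the first reply.

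**The concern.** Item 6 is a protective-factor question: a yes means that something is stopping the person. Item 7 is the danger question. Both escalation lines point to the first and neither points to the second, so the printed trigger is attached to the wrong answer.

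The line is spoken by staff who may not be clinically trained. The script gives them the words "I am not a clinician, but I would like you to talk to one right now". For such a caller the item numbers are the escalation rule. At stake is whether a person in immediate danger is escalated on a live call, and whether emergency services are sent for someone who has just given a reassuring answer. Nothing in the trial's estimates or tests depends on it.

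**Working it through.** No figure in the plan is involved. The check sets the printed items beside the numbers cited in the action lines of section 14.8.

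**Step 1: which items are cited.**

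| Item as printed | Content | Cited in an escalation line |
|---|---|---|
| 1 | method | no (first block only) |
| 2 | plans | yes, jointly with 3 |
| 3 | preparations | yes, jointly with 2 |
| 4 | past attempt | no (first block only) |
| 6 | prevention | yes, in both lines |
| 7 | immediate danger | no, and in no other action line |

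Both escalation lines (2 of 2) cite item 6; 0 of 2 cite item 7.

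**Step 2: the rules as printed and as labelled.**

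- As printed: clinical input if (2 and 3) or 6; emergency step if 6.
- With the emergency line's label taken as the meaning of the number: clinical input if (2 and 3) or 7; emergency step if 7.

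**Step 3: results when items 2 and 3 are not both yes.**

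| Item 6 (something is stopping them) | Item 7 (immediate danger) | As printed | As labelled |
|---|---|---|---|
| yes | no | clinical input and emergency step | neither |
| no | yes | neither | clinical input and emergency step |
| yes | yes | both | both |
| no | no | neither | neither |

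When items 2 and 3 are both yes, clinical input follows in every row, and the emergency column is unchanged. The emergency step therefore goes wrong whenever the answers to 6 and 7 differ. Clinical input goes wrong in those rows only when 2 and 3 are not both yes. The second row is the most worrying pattern: immediate danger with nothing holding the person back.

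**Step 4: where the slip comes from.** If the printed items are numbered without the gap, prevention becomes 5 and immediate danger becomes 6. Both escalation lines then point to immediate danger and agree with the label. The action lines fit a consecutive numbering that the question list does not have. Even if a fifth question were missing from the copy at hand, item 6 would still be prevention and item 7 still immediate danger.

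**Step 5: the email list and the template in section 14.9.**

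- Required list: thoughts (Q1), intention (Q2), plans (Q3), means (Q4).
- Template questions: thoughts, plans, preparations, prevention.
- In both: thoughts and plans, 2 of 4. Required but not asked in the template: intention and means. The template does advise getting rid of the means, but it does not ask whether the person has them.

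**The case against.** The strongest reply is that nobody would follow the bare digit. The label stands next to the number in the emergency line. That line is an addition to the clinical-input line and cites the same number, so the label can reasonably be read as covering both. An unnumbered instruction tells the caller to stay on the line if immediate risk is disclosed. The words scripted after the trigger express strong concern for safety, which makes no sense after a protective answer. The Risk Report Form (Figure 3) has separate named fields for prevention and immediate risk, and section 14.11 is keyed to immediate risk in words. Section 14.7 requires training, a signed delegation log and access to a clinician.

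This stands as far as intent goes. A reader might infer from the literal rules that participants in immediate danger would go without help, or that emergency services would be sent for people who are safe. The document does not support that as an expected outcome, because its surrounding text shows what was meant. What remains is that the clinical-input line carries no label of its own, and a script for non-clinicians on a live call should not leave them to work out that one number means another.

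A reader might also infer that the email route is unsafe because neither the list nor the template asks about immediate danger. Section 14.9 tells staff to "enquire about risk following the questions above (e.g., asking about suicidal ideation, thoughts, plans, preparation, prevention, means", which brings in the telephone questions by reference, with the bracketed topics only as examples. The template is an adaptable first reply, it directs anyone who may not stay safe to emergency care, and follow-up emails are provided for. Leaving acute danger to signposting in an email that may not be read at once is a defensible clinical choice.

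**Conclusion.** The finding holds as a cross-reference error in a safety script. Both escalation lines in section 14.8 cite the prevention item, and the immediate-danger item is cited nowhere. The intent is clear from the label, so the practical risk is smaller than the literal reading suggests, but the printed trigger is wrong and should be corrected. The conclusion rests on the printed numbering and on reading the label as the intended meaning, which consecutive numbering supports.

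The mismatch in section 14.9 between the required questions and the template is minor.

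Three further inferences are not supported. That the Self Risk numbers differ from the telephone numbers is no fault: they carry their own labels and no action line cites them. That the intention question and a no to prevention have no numbered action line is true, but whether they need rules of their own is for the clinical lead, and the document does not contradict itself there. The same goes for asking about past attempts by email.

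**What to change.** In section 14.8, either number the items consecutively (prevention 5, immediate danger 6) and leave the two escalation lines as they are, or keep the numbering and change both lines to cite a yes to item 7. Do one, not both. In either case write the content of the item beside its number in every action line, for example item 7 (immediate danger), so that a later renumbering cannot detach the action from the question.

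In section 14.9, add the intention and means questions to the template so that it contains what the section already requires.

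The cost is a few lines of text, a new version of the procedure, and a short re-briefing of staff already trained on it. The clinical lead should confirm the wording. No data collection or analysis changes.
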